4. STUDY DESIGN

We will conduct study visits in the Schubert clinic to determine and quantify known molecular, genetic, genomic, epigenetics, immunologic, and exposure biomarkers that will help elucidate molecular disease endotype within the DTT phenotype (Figure 1). This information will be used along with clinical, psychosocial, and adherence data to develop

a personalized treatment plan. We will track disease outcome metrics including exacerbations, symptom-free days, and a validated asthma composite control score to determine the effectiveness of this personalized approach (summarized in Figure 1).

A number of interventions will be incorporated based on information collected on questionnaires on personal and family medical history, history of environmental exposures, previous and current residential and school addresses, depression, anxiety, dietary intake, adherence, medical literacy, and perceived quality of life, medical visits, use of a commercially available inhaler cap monitoring sensor, a mobile software management platform that tracks adherence of asthma medications, mobile based telehealth adherence problem-solving interventions, biomarker assays and home trigger assessment and remediation.

This proposal is funded through a CCHMC ARC award.

5. DURATION:

Duration for the participants will be 12 months. We will continue to follow asthma outcomes via the patient's medical record for an additional 12 months. Participants will be enrolled in the study during the 24 months of the project. If additional funds are awarded, the enrollment period may be extended to a third funding year. Data analysis will be performed 6 months after the last participant completes the project.

6. SELECTION & RECRUITMENT OF PARTICIPANTS:

A. Number of participants

Patient Population: 30-50 6-17 year old children with uncontrolled moderate-severe persistent asthma without significant chronic disease other than allergic disorders.

B. Inclusion/Exclusion criteria

Inclusion

- age 6-17 years; history of provider-diagnosed asthma;
- Meets one of the following definition for NAEPP guidelines uncontrolled moderate persistent asthma or severe persistent asthma in the past 12 months:
 - NAEPP step 3-4 with one of the following criteria in the past 12 months:
 - two ACT scores <20
 - ≥ 1 UC/ED visit or hospitalization for asthma
 - ≥ 2 prednisone bursts
 - NAEPP step 5-6

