a participant completes all study activities, this equipment will be collected at the final home visit (H2) or once the self-management visits are completed coordinators will schedule to come pick up the equipment from the family's home. If a participant is discontinued from the study early due to lost to follow-up, study staff will follow the *Study Discontinuation MOP* in order to collect the loaned iPad and Cradlepoint. The actions taken will include: phone calls, text messages, emails, letters mailed to the home, and home visits. If the equipment is not recovered, a certified letter will be sent to the home with instructions to return the iPad and Cradlepoint with a copy of the *Telehealth Agreement Form* that was signed at the first Home Visit (H1). Per the signed *Telehealth Agreement Form*, families are responsible for notifying CCHMC if the iPad is lost or stolen. "iPads that are lost or stolen will be reported to the CCHMC Protective Services Department and to the appropriate Police Department". If the equipment is not returned after all steps in the *Study Discontinuation MOP* have been followed, the Telehealth department at CCHMC will be notified that the equipment was not recovered.

9. DATA ANALYSIS/METHODS:

Study Outcomes:

The adolescent's asthma outcomes and adherence will be measured at baseline and during the clinical visits or study telephone calls once a month for a total of 12 months. Outcomes will be measured during the monthly medical visits using a computerized TreatSmart program based on the NAEPP asthma guidelines which was adapted by the CCHMC Asthma Center database team from the Inner City Asthma Coalition (Appendix C), ACT scores, and Propeller Health web-based inhaler cap monitoring sensor and mobile software management platform (Appendix B).

Primary Outcome:

Composite asthma severity index (CASI) score collected monthly during phone calls, home visits, and clinic visits over 1 year. The CASI is a severity score of symptom burden, exacerbations, healthcare utilization, lung function and dose of inhaled corticosteroids. This score will be collected and captured by the TreatSmart program.

Secondary Outcomes:

We will analyze the following outcomes: ACT score over past 4 weeks; rescue medication use, oral-steroid requiring exacerbations; healthcare utilization, lung function, dose of inhaled corticosteroids, and adherence of controller medication.

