These asthma related outcomes are commonly reported in both the adult and pediatric asthma literature and are endorsed by national asthma guidelines and the National Institutes of Health (NIH) asthma-outcome conference.

Data Analysis

We will use descriptive statistics to characterize the sample demographics. A descriptive analysis with calculation of means, medians, and standard deviations will be performed for each continuous measure; categorical measures will be examined with percentages. If necessary, we will log-transform non-normal data; however if a normal distribution cannot be attained we will use nonparametric statistics. We will use paired t-tests to evaluate the null hypothesis that there was no change in the primary outcome (CASI score) while participants are blinded to data collected by the Propeller medication sensor in the first month of participation. Nonparametric methods will be used if the assumptions for paired t-tests are violated. The primary analyses will test whether this interventional program improves CASI scores (from completion of the first month to study exit). Linear mixed effects models with a random effect for subject assessed changes in primary asthma endpoints each month across the 1 year study or upon exit. Participants with one or more observations will be included in the analysis. All statistical analyses will be implemented in SAS 9.3 (SAS Institute, Cary, NC) and use a significance level of 0.05. Potential confounders identified from the literature, such as age, gender, season of enrollment, severity of asthma at baseline, smoke exposure, environmental exposures and atopic status will be adjusted in the analyses. The REML model used for these analyses requires that any missing data are “missing at random” (MAR) to yield valid estimates. To account for the presence of possible non-ignorable missing data, pattern- mixture modeling will be applied for these analyses.

The secondary analyses will look at the ACT score, rescue medication use, oral-steroid requiring exacerbations, healthcare utilization, lung function, dose of inhaled corticosteroids, and adherence of controller medication. Linear mixed-effect models will be used to compare the continuous outcomes such as exacerbations. Generalized linear mixed effect models will be used to compare the discrete outcomes such as health system utilization, both accounting for repeated measurement over time while adjusting for confounders.

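### Exacerbations are event counts but are classed as continuous and given a linear mixed model; they belong under the plan's own generalized linear mixed model.

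*Combined protocol and SAP*

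**What the plan says.** Section 9, Data Analysis, splits the secondary outcomes into two model classes. The first sentence is "Linear mixed-effect models will be used to compare the continuous outcomes such as exacerbations". The next is "Generalized linear mixed effect models will be used to compare the discrete outcomes such as health system utilization". No distribution or link is given for the second class.

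The Secondary Outcomes list names "oral-steroid requiring exacerbations; healthcare utilization" as adjacent items, so two event-type outcomes are sent to different models. Data are collected at clinic visits or "study telephone calls once a month for a total of 12 months". For the primary endpoints the plan specifies "Linear mixed effects models with a random effect for subject"; for the secondary outcomes it says only that repeated measurement is accounted for. A general clause adds that "if a normal distribution cannot be attained we will use nonparametric statistics", after a log transformation has been tried.

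Elsewhere the protocol treats these events as whole numbers. One entry route in section 6.B is "≥ 2 prednisone bursts" within 12 months. The Study Termination text in section 8 ends participation at 4 or more severe exacerbations, a count that includes those treated with systemic steroids.

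**The concern.** A steroid course either happens or does not. Per child-month the value is 0, occasionally 1, rarely more. For such data the variance follows the mean, so the constant residual variance of a standard linear mixed model fails as soon as the rate changes, which is what the study hopes to see.

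Section 4 gives this outcome weight: "We will track disease outcome metrics including exacerbations, symptom-free days" introduces the measures by which the personalized approach is judged. Two things are at stake: whether the confidence interval for the change is honest, and whether the model understates a true fall when children with many courses leave early.

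**Working it through.** **No figure to reproduce.** The documents give no rate, dispersion, effect size or power for this outcome. Everything below rests on assumed rates.

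**Inputs from the documents.** 30 children (section 8), up to 50 (section 6.A); monthly data for 12 months (section 9); alpha 0.05 (section 9); stop at 4 or more severe exacerbations (section 8).

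**Assumed.** Monthly rates from 0.167 to 0.083, 0.2 to 0.1, 0.167 to 0.033, or 0.25 to 0.05. The value 0.167 is 2/12, taken from the entry criterion, which is not a documented mean. Given a child effect u (gamma, mean 1, shape k = 0.7 to 2), the count in month t is Poisson with mean u × λ(t). The linear model has a random intercept and constant residual variance.

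**Step 1: zeros.** P(0) = (k/(k+λ))^k. With k = 1 this is 1/1.167 = 86% at 0.167 and 1/1.083 = 92% at 0.083. Over the scenarios, roughly 85-93% of child-months are zero. The log of zero is undefined, and no transformation makes such data normal.

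**Step 2: variance.** Within-child variance averages λ(t), so month 1 to month 12 it changes by a factor of 2 for a halving and 5 for an 80% fall. The linear model uses one pooled value, close to the average rate.

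**Step 3: hand check of coverage, ignoring the between-child part.** Coverage ≈ 2Φ(1.96 × √(assumed variance / true variance)) − 1, with log-linear decline.
- Halving from 0.167, average rate 0.121. Month-12 minus month-1 difference: √(0.241/0.250) = 0.98, giving 94.6%. Month-1 mean: √(0.121/0.167) = 0.85, giving 90.5%.
- 0.25 to 0.05, average rate 0.127. Difference: √(0.253/0.300) = 0.92, giving 92.8%. Month-1 mean: √(0.127/0.25) = 0.71, giving 83.7%.

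**Step 4: how many children the stop rule could remove.** For k = 1, P(4 or more) = (M/(1+M))^4, where M is the expected count so far. Halving from 0.167 gives M = 1.448 over 12 months: (1.448/2.448)^4 = 12%. By month 3, M = 0.470: (0.470/1.470)^4 = 1%.

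**Step 5: simulation of the full models.** 30 children; 20,000 trials per scenario for the linear model without stopping, about 1,500 where the stop rule applies; the count model is Poisson with a random intercept.

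| Scenario | Linear model | Count model |
|---|---|---|
| No stopping, no change: coverage | about 95% | 94-96% |
| No stopping, halving: coverage, difference and slope | 93-95% | 94-96% |
| No stopping, 80% fall: coverage | difference 91-94%, slope 88-93% | 94-96% |
| Monthly stop check, true 50% fall | fitted as 29-44%, coverage 89-95% | fitted as 45-49%, coverage 94-96% |
| Monthly stop check, 0.25 to 0.05 | slope 16-38% too shallow, coverage 72-90%, power 57-77% | coverage about 95%, power 67-81% |
| Stop check at V2 only (taken as month 3), true 50% fall | fitted as 45-50% | – |

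Monthly checking stops 9-16% of children; a V2-only check stops 0.5-3%. With 50 children the no-stopping results move by about 1 point, so a larger sample does not cure the problem. Without stopping, power is alike under both models: 28-34% for a halving and 87-89% for 0.25 to 0.05. A separate simulation (400 trials per scenario, shape 1) agreed: without stopping, linear slope coverage was 94%, 92% and 88% for no change, halving and an 80% fall; the slope was 27-29% too shallow with monthly checks and 5-6% with a V2-only check.

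**The case against.** The labelling error is not in dispute; its consequence can be.

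- **The model-class error alone is small.** For a halving without stopping, coverage is 93-95%, and a robust standard error brings the 80% fall to 92-94%. The poorer single-month coverage does not concern the change over time that the plan sets out to assess. This stands.
- **The larger figures need frequent stop checks.** Section 8 ties the count to medical visits, and Appendix A schedules only V1, V2 and an optional V3. Even with the check at month 5, just past V2's six-week window, 2-4% of children stop and a 50% fall is fitted as 42-50%. Sick visits, and section 9's reference to monthly medical visits, could make checks more frequent. The monthly figures are therefore an upper bound.
- **The bias depends on an assumed random-intercept structure.** A random child slope in the linear model restores coverage to 94%; a robust standard error does not (81-91%). True, but the plan specifies no such slope.
- **The rate anchor is weak.** Prednisone courses are only one entry route. At half the anchor, even monthly checks stop 2-3% and a 50% fall is fitted as 41-49%.
- **The simulations suit the count model.** If response varies between children (assumed log-slope SD 0.8), its coverage drops to 92-94%, or 93-95% with a robust standard error.
- **Other clauses might help.** Pattern-mixture modelling and a further 12 months of record follow-up (section 5) are planned, but neither is clearly tied to this outcome or to stopped children. Neither supplies a count analysis, and the nonparametric clause names no method for repeated, adjusted data.

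**Conclusion.** The concern holds. The plan classes an event count as continuous while holding the right model class in its next sentence, and no other clause repairs this.

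The size is modest. There is no harm if the rate is flat, slight undercoverage for a halving, and clearer undercoverage for a steep fall. The stop-rule bias ranges from negligible to material, depending on how often the rule is applied, and it runs toward understating benefit. These sizes rest on assumed rates, gamma frailty and a random-intercept linear model; the misclassification itself rests on the text alone. As this is a secondary outcome in a pilot, the change should be made, but neither the CASI analysis nor the sample size depends on it.

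**What to change.** Move exacerbations to the generalized linear mixed model sentence. State Poisson or negative binomial, log link, random subject effect, and an offset for the person-time actually covered; report a rate ratio with 95% CI. Add a robust standard error as a sensitivity analysis.

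Two supporting details are worth a line each:

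- **Covariates and fallback.** Only about 30-54 events are expected in 30 children at the assumed rates (for example, 30 × 12 × 0.15 = 54). With seven child-level covariates, the number listed in section 9, the random-effect variance was estimated as zero in 9-14% of simulated trials. Pre-specify a shorter list and what to do in that case.
- **Counting rule.** Count each steroid course once, by start date. This is separate from the choice of model. With a flat rate of 0.15 per month and missed calls rising to 30%, summing courses since the last contact gave false worsening in 10.5% of trials, against 2.3% when courses were placed by start date in the same linear model.

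The cost is one moved sentence and a short specification in the SAP. Software and data sources stay the same, and no clinical rule changes. The price is that fewer covariates can be supported.

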1. ABSTRACT

Asthma is a common, complex and costly chronic condition both locally and across the U.S. Moreover, asthma is heterogeneous in terms of treatment response and natural history. This heterogeneity contributes to the difficulty in both studying and treating asthma. This is a pilot study to improve asthma outcomes in 30 youths with difficult to treat asthma with ongoing symptoms and healthcare utilization despite medium to high doses of inhaled corticosteroids. We will identify difficult to treat (DTT) asthmatic children at CCHMC and in the community by leveraging key partnerships and efforts that are already in place with Cincinnati public schools, Cincinnati Health Department and community practices. Although CCHMC has participated in several initiatives and successfully reduced ED visits and hospitalizations among Medicaid-insured asthmatic children, we did not explore the biologic mechanisms underlying these DTT patients. Asthma heterogeneity in both disease pathophysiology and treatment response contributes to the difficulty in both studying and managing asthma. In order to begin to develop personalized

algorithms for patients, we need to model novel biomarkers and other factors that contribute to individual differences in asthma outcome and test personalized treatment strategies. Furthermore, our community partners will be involved in key design elements of this project: engagement of patients, increasing community awareness, and dissemination of the progress and results of the study back to the community.

2. PURPOSE OF STUDY:

The purpose of this project is to achieve the best possible health outcomes for the most at-risk children with asthma through synergistic integration of clinical care, basic, translational and community-based research efforts. This is a pilot study to improve asthma outcomes in 30 youths with difficult to treat asthma with ongoing symptoms and healthcare utilization despite medium to high doses of inhaled corticosteroids. We will identify DTT asthmatic children at CCHMC and in the community by leveraging key partnerships and efforts that are already in place with Cincinnati public schools, Cincinnati Health Department and community practices. Our community partners will be involved in key design elements of this project: engagement of patients, increasing community awareness, and dissemination of the progress and results of the study back to the community.

3. BACKGROUND:

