Asthma is a common, complex and costly chronic condition in the U.S., resulting in nearly 2 million acute care visits and \$56 billion in overall costs each year (Akinbami 2012). Of these patients, 5-20% have poorly controlled asthma accounting for nearly 50% of all asthma-related expenditures (Pakhale 2011). Both nationally and locally, minority and disadvantaged children have the highest prevalence of asthma and the greatest disparities in asthma morbidity and mortality. Within Hamilton County, over 36,000 children have asthma, >14,000 of whom are Medicaid-insured with a 10 fold higher rate of hospitalization. Moreover, asthma is heterogeneous in terms of treatment response and natural history. This heterogeneity contributes to the difficulty in both studying and treating asthma. We have already developed successful, collaborative programs (as part of SP2015) with General and Community Pediatrics, community agencies, Hospital Medicine, Pulmonary Medicine to reduce ED visits and hospitalizations among Medicaid-insured asthmatic children, sustaining a >20% reduction in ED visits and hospitalizations since 6/2015. Although this work targeted high-risk patients, we did not explore the biologic mechanisms underlying these difficult to treat (DTT) patients. Asthma heterogeneity in both disease pathophysiology and treatment response contributes to the difficulty in both studying and managing asthma. In order to begin to develop personalized algorithms for patients, we need to model novel biomarkers and other factors that contribute to individual differences in asthma outcome and test personalized treatment strategies. Our proposal is highly innovative in that it will provide a basis for molecular sub-classification of the DTT asthma endotype and provide a foundation and framework for the development and implementation of multi-modality treatment strategies specifically designed for this high-risk/cost subgroup. We have the opportunity to become the national/international leader in pediatric asthma activities spanning discovery to new treatments and novel health delivery systems.

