If a consent/assent form is updated and requires a new signature, coordinators will go over the changes via either a scheduled monthly phone call or scheduled study visit (depending on which visit occurs first) and participants and guardians may be re-consented by either eConsent (as stated in the section above) or by signing a copy of the consent/assent either in person or sent through the mail. Participant's and guardians will be given ample time to read through the new consent/assent and will be able to call and ask questions etc. once they have been able to read through the consent/assent.

For participants under age 18, age of assent will be determined by the IRB and those assenting will sign after all questions are answered.

For non-English speaking participants

Because this is a small pilot and heavily dependent on English fluency for teleconference interviews and questionnaires, only participants who are fluent in English will be enrolled. If a parent is non-English speaking, the PI will determine if the subject can be enrolled based on subject's fluency. If a non-English speaking parent will be giving Parental Permission, the research team will use a short form consent process as per CCHMC SOP 41-1.8. The approved long consent form will serve as the summary of the research.

8. STUDY PROCEDURES:

See Appendix A.

The study length is 12-15 months. 30 participants will be enrolled over a 9 month period. Propeller and TreatSmart program screenshots are located in Appendix B and C.

CCHMC Visit 1 (V1)- Baseline Medical Visit: This visit will be conducted at CCHMC.

The coordinator will consent the parent/legalguardian(s) and (if applicable) obtain assent from the child/adolescent. Baseline questionnaires will be completed by a parent/guardian and the participant, and the study visit procedures will be explained by the study coordinator.

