- Dust/air sampling: Household dust samples will be collected and banked at CCHMC. A dust sample will be taken from the child's bedroom and/or the child's primary activity room by the trained research coordinator. These samples will be collected into a filter fitted onto a vacuum hose. The carbon filters from the provided air purifier will be collected every 3 months and returned to the study staff for dust analysis. The dust samples may be analyzed for biomarkers of exposure or disease, including but not limited to allergen levels, air pollution, microbiome and mold. These factors will be included as potential predictors of disease development

and severity, and will also be analyzed in conjunction with biospecimen data (such

as serum cytokines and vitamin D levels, genetic polymorphism, gene expression and methylation levels, etc.) and personal and demographic characteristics.

- Dispense home trigger remediation package equipment and materials (dust mite mattress and pillow covers, cleaning supplies, HEPA filter and HEPA vacuum) & provide family with necessary training/education.

Propeller Health Inhaler monitoring and Web-based Platform

Propeller Health, a web-based inhaler cap monitoring sensor and mobile software management platform will be used to monitor how frequently the participant uses their inhaled asthma medication (Appendix B). The monitoring cap will be placed on both the controller and rescue inhalers by the study team at the first home visit (H1) and they will be registered with Propeller Health. The inhaler use will be recorded on the web platform. Starting the time of the initial self-management intervention session at month 3½, a mobile-based app program will be available for both android and IOS platforms and will allow the participant and family to interact directly with the platform. This is a FDA approved, HIPAA compliant device that has been demonstrated to improve asthma outcomes and adherence measures. This equipment has been approved by the CCHMC Equipment committee for use in prior studies. A contract and data use agreement was also approved for prior studies and will be reviewed and updated for the purposes of this study. Propeller Health may collect User PHI or PII and Usage Data from each user and generate de-identified data reports in accordance with the terms and conditions of the data use agreement signed by Propeller Health and CCHMC.

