These results will be used to inform cluster analysis to determine the combinations of biomarkers and that are most predictive of the CASI scores and clinical outcomes.

Future use

The de-identified data may be used for future research, analysis or recruitment. Audio recordings from the self-management visits will be destroyed following completion of the study. All re-identification codes will be destroyed.

10. FACILITIES and PERFORMANCE SITES:

The Cincinnati Children's Hospital and Medical Center CCHMC Pulmonary and Asthma Research Divisions, and CTCRC.

11. POTENTIAL BENEFITS:

Participants will have direct benefit of being closely monitored for their asthma and clinical care. The future benefit is to determine if a personalized plan of medications and home environmental trigger remediation plan based on environmental evaluation, all biomarker assays and self-management assessments can improve asthma outcomes in neighborhoods where the incidence of asthma is especially high.

12. POTENTIAL RISKS, DISCOMFORTS, INCONVENIENCES AND PRECAUTIONS:

The risks to participants are minimal and include:

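### Cluster analysis is the only method named for finding which biomarkers predict CASI; in its ordinary sense it does not use the outcome, and no outcome-directed model or internal validation is planned

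*Combined protocol and SAP*

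**What the plan says.** Section 9 (Data Analysis) gives the biomarker-outcome analysis one sentence. It begins "These results will be used to inform cluster analysis" and states the purpose as "cluster analysis to determine the combinations of biomarkers and that are most predictive of the CASI scores and clinical outcomes". The sentence appears to lack a word. It names no algorithm, inputs, number of clusters, stability check, marker-selection rule, performance measure or validation.

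The mixed models described just before it adjust for age, gender, season, baseline severity, smoke and environmental exposures and atopic status. They do not enter molecular biomarkers as predictors. The significance level is 0.05, with no provision for multiple markers.

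The candidate markers are open-ended. Section 4 refers to "known molecular, genetic, genomic, epigenetics, immunologic, and exposure biomarkers". Section 8 (Home Visit 1, dust/air sampling) says of the dust measures "These factors will be included as potential predictors of disease development", again without a model.

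Prediction is a stated motive for the study. Sections 1 and 3 both say "we need to model novel biomarkers and other factors that contribute to individual differences in asthma outcome". Section 3 also has a separate aim, molecular sub-classification of difficult-to-treat asthma.

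On size, section 1 has "This is a pilot study to improve asthma outcomes in 30 youths with difficult to treat asthma", section 8 has "30 participants will be enrolled over a 9 month period" and section 6A has "30-50 6-17 year old children with uncontrolled moderate-severe persistent asthma".

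**The concern.** The named method and the stated aim do not match. Clustering describes which children or markers resemble each other. Saying which combinations best predict CASI requires a model with CASI as the response and a measure of how well it predicts children who were not used to build it. The plan has neither.

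An analyst following the text would have to improvise the missing step. One route is to form clusters and compare CASI between them, which tests the cluster split and does not search for predictors. Another is to pick the markers that fit CASI best and report that fit. With few children and many markers, the second route gives impressive figures from noise. A pilot is meant to guide later work, so a false lead here is the main cost.

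**Working it through.** **Inputs.** The plan gives no marker count, effect size or sample-size calculation, so it has no figure to reproduce. From the documents: n = 30 (sections 1, 2, 8) and n = 50 (upper end, section 6A); significance level 0.05 (section 9), taken as two-sided. Assumed: the number of markers, their correlations and all effect sizes.

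**Step 1: what clustering uses.** A standard algorithm such as k-means minimises the distance between marker profiles within groups. CASI is not in that criterion, so the same clusters result whatever the CASI values are. Any statement about prediction needs a further step, and section 9 does not give one.

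**Step 2: what appears if CASI is compared between clusters afterwards.** Simulation with 400 runs, n = 30, 50 markers, three of them carrying half of the CASI variance, and a correlated block of 15 markers (correlation 0.6). Two-group k-means with a t-test on CASI is set beside a marker-by-marker screen at a 5% false discovery rate (FDR).

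| Where the signal lies | Clusters differ in CASI, p<0.05 | FDR screen flags at least one marker |
|---|---|---|
| Outside the block; signal markers independent, up to correlation 0.5 | about 5-9% | about 36-88% |
| Inside the block | about 88% | about 93-95% |

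A second illustration (1,000 runs, n = 30) has ten markers forming two clusters and an eleventh correlated 0.7 with the outcome. The clusters explain 3.7% of outcome variance, against 1/(n-1) = 1/29 = 3.4% by chance; the eleventh marker alone explains 49%. If the clusters align with the outcome, they explain about 50%. Clustering therefore shows a link with CASI when the dominant structure carries it, and otherwise does not.

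**Step 3: apparent fit when markers are chosen by fit.** Markers unrelated to the outcome; take the five with the largest absolute correlation, fit them by least squares and record R-squared (400 runs; repeat runs moved these by no more than about 0.02).

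| Noise markers (assumed) | n = 30 | n = 50 |
|---|---|---|
| 50 | 0.48 | 0.32 |
| 200 | 0.59 | 0.44 |
| 1000 | 0.70 | 0.53 |

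For comparison, five noise markers fixed in advance have expected R-squared p/(n-1): 5/29 = 0.17 and 5/49 = 0.10. The rest is due to selection.

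A smaller search, for the best pair among noise markers, shows what happens in new data. A negative value means worse than predicting the mean.

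| Noise markers | n = 30, apparent | n = 30, new data | n = 50, apparent | n = 50, new data |
|---|---|---|---|---|
| 10 | 0.21 | -0.30 | 0.12 | -0.15 |
| 50 | 0.35 | -0.50 | 0.22 | -0.28 |

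**Step 4: what a clean analysis could detect.** For one prespecified marker, the correlation detectable with 80% power is r = tanh[(1.960 + 0.842)/√(n-3)].

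- n = 30: tanh(2.802/5.196) = tanh(0.539) = 0.49.
- n = 50: tanh(2.802/6.856) = tanh(0.409) = 0.39.

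Even a well-specified analysis will find only large associations.

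**The case against.** The strongest reply is that one incomplete sentence in a pilot plan is being read too closely. It does not say the clustering ignores CASI, and an outcome-guided variant is not formally excluded. A common two-step approach forms clusters and then compares CASI across them, perhaps with the section 9 mixed models. Clustering also suits the sub-classification aim in section 3. Biomarker prediction is neither the primary nor a listed secondary outcome.

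Much of this stands, and it rules out several stronger readings that a reader might infer:

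- **That clustering would almost always miss the predictive markers.** Step 2 shows this depends on where the signal lies. The documents do not say, and an endotype hypothesis would place it inside the cluster structure.
- **That the same children would first select and then confirm the markers.** The text says only that earlier results inform the clustering. It describes no selection or confirmation step.
- **That 30 children make validation impossible.** Resampling-based internal validation can be done at that size. The gap is that none is planned.
- **That the endotype question goes unanswered.** Descriptive clustering can address it. The question left open is prediction.

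What the reply does not remove is the mismatch. No outcome-guided variant or follow-up comparison is named, and comparing CASI between clusters would still not identify the most predictive combinations.

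**Conclusion.** The point holds for the prediction aim. The only named method does not, in its ordinary sense, use the outcome, and the plan has no outcome-directed biomarker model and no internal validation. If markers were picked by apparent fit, chance alone would give a best-five R-squared of about 0.48 to 0.70 at n=30 and 0.32 to 0.53 at n=50, for an assumed 50 to 1000 independent noise markers. These figures illustrate the hazard under those assumptions and do not forecast this trial's results. The conclusion is the same at 30 and at 50 children.

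This is an exploratory aim of a pilot. A reader might infer that the main result is at risk, but the primary CASI analysis in section 9 does not depend on the cluster analysis and is unaffected. The change is worth making because it is cheap and protects whatever work follows.

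**What to change.** In section 9, separate the two aims.

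1. **Endotype description.** Keep cluster analysis, built from markers without the outcome. State the inputs, the algorithm, how the number of clusters is chosen and a stability check. Any comparison of CASI between clusters is descriptive.
2. **Prediction.** List a short set of baseline markers before outcome data are examined. Model baseline CASI and change in CASI on that set, for example by penalised regression, or by univariate models with FDR control. Repeat all selection and tuning inside cross-validation or bootstrap optimism correction. Report the corrected R-squared and a permutation p-value.
3. **Label.** Call the prediction result hypothesis-generating, and state how many markers were considered.

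The choice among these models is partly preference; the essential parts are the prespecified list, a model with CASI as the response, and validation that includes the selection step.

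The cost is plan wording and modest analysis time, with no new data. The corrected R-squared will be lower than the apparent one, imprecise at this size and possibly near zero.
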